#### Follow-up adjusted incidence rate

Follow-up adjusted incidence rate will be summarized by system organ class and preferred term by study group. Follow-up adjusted incidence rate, defined as the number of subjects who experienced an event divided by the total of entire follow-up time among the subjects in the analysis population. The entire follow-up time for subject is defined as the time from the first dose until the end of study day. Each subject will be counted only once within each category. A similar table will also be based on total number of events divided by the total of entire follow-up time among the subjects in the analysis population. This may count a subject more than once within each category if they experienced an event more than once.

#### Note on capture of severity and seriousness in CS4

In CS4 the eCRF captured detail for each investigator term for decreases in severity and changes from serious to non-serious. In 232SM203, the decrease in severity and change from serious to non-serious is not captured. In all studies worsening in severity and moving from non-serious to serious is captured.

In presenting CS4 as part of 232SM203 reporting, consistent with how these studies were originally reported in the following two scenarios:

- 1) where the severity decreases
- 2) where a serious event becomes non-serious

Product: Nusinersen	Statistical Analysis Plan
Study: 232SM203	Version: 1.0

Only the first record will be considered treatment emergent so the actual reporting approach will be consistent with 232SM203.

#### 6.1.1. Concomitant therapy and Procedure

A concomitant therapy is any drug or substance administered between screening and the final study visit/telephone call. Participants are instructed to contact their Investigators before taking any new medications, including nonprescription drugs and herbal preparations.

Throughout the study, Investigators or designated licensed physicians involved in the study may prescribe concomitant therapies (procedures) or treatments deemed necessary for AEs or to provide adequate supportive care.

Participants are prohibited from receiving other experimental or approved agents for the

treatment of SMA, including gene therapy, biological agent, or device, during the study. This includes marketed agents at experimental doses that are being tested for the treatment of SMA (oral albuterol/salbutamol, riluzole, carnitine, sodium phenylbutyrate, valproate, hydroxyurea, etc.).

All concomitant therapies will be coded using the World Health Organization drug

dictionary (WHO Drug). A concomitant procedure is any therapeutic intervention (e.g., surgery/biopsy, physical therapy) or diagnostic assessment (e.g., blood gas measurement, bacterial cultures) performed between Screening and the final study visit/telephone call. Concomitant procedures will be coded using MedDRA.

For the purposes of analysis, a concomitant therapy (including medication or procedure) is defined as any therapy that was taken or administered on or after the first injection of nusinersen. (appendix A). This includes therapies and procedures that were started prior to the initiation of injection of nusinersen if their use continued on or after the first injection of nusinersen. The number and percentage of subjects who were taking each type of concomitant therapy and procedures at baseline and during the study will be presented by preferred term.

The number and percentage of subjects who underwent each type of concomitant procedure during the study will be presented.

Concomitant therapies related to LP/Sham procedure will be summarized separately.

If there are a sufficient number of tests or treatments reported with indication of COVID-19, a separate summary of these will be provided.

Concomitant medications will also be reviewed by a medical reviewer prior to the lock to determine disallowed medications according to the protocol. These will be summarized separately.

# 6.1.2. Clinical laboratory data

Laboratory data will be evaluated to determine the incidence of abnormalities that emerge during the course of the study. Changes in laboratory evaluations will be presented relative to baseline, which is defined as the closest visit prior to the first dose.

Product: Nusinersen	Statistical Analysis Plan
Study: 232SM203	Version: 1.0

The following clinical laboratory parameters are to be assessed:

- Hematology panel: complete blood count with differential and platelet count (hematocrit, hemoglobin, platelets, red blood cell count [RBC], white blood cell count [WBC], basophils, eosinophils, lymphocytes, monocytes, neutrophils)
- Blood chemistry panel: albumin, total bilirubin, direct and indirect bilirubin, alkaline phosphatase, alanine aminotransferase (ALT) (SGPT), aspartate aminotransferase (AST) (SGOT), gamma-glutamyl transferase (GGT), sodium, potassium, calcium, chloride, phosphate, blood urea nitrogen (BUN), creatinine, cystatin, creatine phosphokinase, creatine kinase, bicarbonate (CO2), glucose, total protein.
- Urinalysis: specific gravity, pH, protein, glucose, ketones, bilirubin, blood, red blood cells, white blood cells, epithelial cells, bacteria, casts and crystals
- Urine total protein assessed by local laboratories CSF analysis: RBC, WBC, protein, glucose.
- Coagulation: PT (prothrombin time), aPTT (activated partial thromboplastin time), and INR (international normalized ratio).

Each hematology, blood chemistry, coagulation and CSF laboratory parameter will be flagged as "low", "normal" or "high" relative to the parameter's normal range or as "unknown" if no result is available.

For each urinalysis laboratory parameter, the number and percentage of subjects experiencing postdose shifts to abnormal will be summarized.

For each hematology, blood chemistry, coagulation and CSF parameter, the number and percentage of subjects experiencing postdose shifts to 'low' or 'high' will be summarized. In each summary, the denominator for the percentage is the number of subjects at risk for the shift. The number at risk for the shift to low is the number of subjects whose baseline value was not low and who had at least one post baseline value. The number at risk for the shift to high is the number of subjects whose baseline value was not high and who had at least one-post baseline value. Subjects will be counted only once for each parameter and each shift regardless of how many postdosing assessments had that type of shift. All post baseline data will be used in the shift tables, regardless of whether a scheduled or unscheduled visit.

Also, for each parameter, the incidence of shift to low will be summarized using the minimum post baseline values. Shift to low includes subjects with a normal, high, or unknown baseline value and at least one post baseline value of the given test. Similarly, the incidence of shift to high will be summarized using the maximum post baseline values. Shift to high includes subjects with a low, normal, or unknown baseline value and at least one post baseline value.

To evaluate potential serious hepatotoxicity subjects with a post baseline AST and/or ALT value  $\geq 3$  times the upper limit of normal (ULN) and a post baseline bilirubin value  $\geq 2$  times ULN at any time, not necessarily concurrent, will be listed with their values. In addition, a plot will be presented with each subject's maximum post baseline AST or ALT value relative to the ULN

Product: Nusinersen	Statistical Analysis Plan
Study: 232SM203	Version: 1.0

against the subject's maximum post baseline bilirubin value relative to the ULN; values do not have to be concurrent. All post baseline data will be used to identify abnormalities, regardless of whether a scheduled or unscheduled visit.

Summary statistics for actual values and change from baseline in laboratory values will be summarized by treatment group and visit. Box plots for chemistry, hematology and CSF showing mean value for each treatment group at each visit will also be presented.

Due to the impact of the COVID-19 pandemic on transport infrastructure, public health or humanitarian emergencies, certain sites may only be able to test blood and urine samples at a local laboratory instead of central one. The use of local labs which will use different techniques/equipment and reference ranges may introduce variability in the results.

To assess the variability of the results two summaries will be presented for actual and change from baseline by visit:

- summarize local laboratory and central laboratory results together
- summarize only central laboratory results

Listings of all chemistry, hematology, coagulation, CSF, urinalysis values and pregnancy test (serum and urine) will be provided.

For platelets a summary of the proportion of participants with a post baseline platelet count below the lower limit of normal on at least 2 consecutive measurements will be presented.

For study 232SM203, the urine protein positive (trace, +1, +2, +3, +4 or >0.2g/L) results will be presented, number of subjects with positive result at baseline, with a negative result at baseline and at least one and at least two positive post baseline result respectively.

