#### **Secondary Safety Objectives**

To examine the safety and tolerability of nusinersen administered intrathecally at higher doses to participants with SMA.

Secondary Safety Endpoints

- Incidence of AEs, including SAEs
- Shifts from baseline in clinical laboratory parameters, ECGs, and vital signs
- Change in growth parameters
- Shifts from baseline in coagulation parameters (aPTT, PT, and INR)
- Change in urine total protein
- Change from baseline in neurological examination outcomes
- The proportion of participants with a post baseline platelet count below the lower limit of normal on at least 2 consecutive measurements
- The proportion of participants with a post baseline QTcF of > 500 msec and an increase from baseline to any post baseline timepoint in QTcF of > 60 msec

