Summary statistics for actual values and change from baseline in laboratory values will be summarized by study group and visit. Line plots for chemistry, hematology and CSF showing median value for each study group at each visit will also be presented.

For a parameter if the local and central result are available with the same date and time then only the central analysis result will be considered for presentations by visit. In a situation where two or more results have the same date and time and are both central (or both local) then we will check with the Safety physician if it would be more appropriate or take the highest or lowest value.

Listings of all chemistry, hematology, coagulation, CSF, urinalysis values and pregnancy test (serum and urine) will be provided.

For platelets a summary of the proportion of participants with a post baseline platelet count below the lower limit of normal on at least 2 consecutive measurements will be presented.

The urine protein positive (trace, +1, +2, +3, +4 or >0.2g/L) results will be presented, number of subjects with positive result at baseline, with a negative result at baseline and at least one and at least two positive post baseline result respectively.

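### The urine protein table shows neither the grade reached nor any worsening in subjects already positive at baseline

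*SAP*

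**What the plan says.** In the Part B later-onset SAP, Section 6.1.2, the only table written specifically for urine protein reads: "the urine protein positive (trace, +1, +2, +3, +4 or >0.2g/L) results will be presented, number of subjects with positive result at baseline", and then those "with a negative result at baseline and at least one and at least two positive post baseline result respectively". The Part B infantile-onset SAP (Section 7.1.3) has the same sentence, and the Part C SAP (Section 5.7.2) repeats it: "The urine protein positive (trace, +1, +2, +3, +4 or >0.2g/L) results will be presented".

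Section 6.1.2 also plans three other displays that touch urine:

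- a shift display: "For each urinalysis laboratory parameter, the number and percentage of subjects experiencing postdose shifts to abnormal will be summarized";
- by-visit summaries: "Summary statistics for actual values and change from baseline in laboratory values will be summarized by treatment group and visit";
- listings: "Listings of all chemistry, hematology, coagulation, CSF, urinalysis values and pregnancy test (serum and urine) will be provided".

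The endpoint that these displays serve is "Change in urine total protein". It is a secondary safety endpoint in both Part B SAPs and a primary endpoint in Part C (Section 2.1).

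**The concern.** The results are recorded in ordered grades, but the table reduces them to positive or negative and sets the cut at the lowest grade. This loses two kinds of information. Among subjects negative at baseline, a single trace result and a +4 are counted alike. Among subjects already positive at baseline, nothing that happens later is reported, so a rise from trace to +4 looks the same as a stable trace.

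The endpoint is a change, yet for every baseline-positive subject the table reports only a starting status. A rise in grade in the higher-dose arm that occurred partly in such subjects, or that showed as higher grades and not as more positives, would not appear in the endpoint's own table.

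**Working it through.** The plan states no expected rate, power or sample size for urine protein, so there is no figure of its own to reproduce. Three checks follow.

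**1. Which worsening moves the table registers.** The scale has six levels: negative, trace, +1, +2, +3, +4. The number of upward moves is 6 × 5 / 2 = 15.

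- From negative: 5. All enter the row for at least one later positive (and the second row if repeated), with no distinction between negative to trace and negative to +4.
- From trace or higher: 4 + 3 + 2 + 1 = 10. None is registered as worsening. The subject appears only in the positive-at-baseline row.

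**2. Whether the other displays close the gap.**

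- Shift to abnormal: it has no grades. The low, normal and high flags and the at-risk denominators in Section 6.1.2 are given for hematology, chemistry, coagulation and CSF, and abnormal is not defined for urinalysis. If trace is abnormal there, trace to +4 is not a shift. If trace is normal, it is.
- By-visit actual value and change: this covers numeric urine protein results. A dipstick grade has no mean change.
- General rule for categorical endpoints (Section 4.4): it could give the percentage in each grade by visit, but it does not name urine grades. It would also not link a subject's baseline grade to that subject's worst later grade.
- Listings: every value is there, subject by subject, but not summarised by arm.

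Elsewhere the same SAP keeps severity visible: QTcF above 480 to 500 is separated from above 500 msec (Section 6.1.4), and systolic pressure above 140 from above 160 mmHg (Section 6.1.5).

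**3. Sensitivity to background trace results.** Neither the per-sample rate of trace or more, p, nor the number of post-baseline urine samples, k, is given. Both are assumptions here: p from 1% to 20%, and k = 7 (the seven post-baseline visits in the safety windows of Section 4.4) or k = 4, with samples independent and no drug effect. For a baseline-negative subject:

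- P(at least one positive) = 1 − (1 − p)^k
- P(at least two) = 1 − (1 − p)^k − k·p·(1 − p)^(k−1)

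| p | k = 7, at least one | k = 7, at least two | k = 4, at least one | k = 4, at least two |
|---|---|---|---|---|
| 1% | 6.8% | 0.2% | 3.9% | 0.1% |
| 5% | 30.2% | 4.4% | 18.5% | 1.4% |
| 10% | 52.2% | 15.0% | 34.4% | 5.2% |
| 20% | 79.0% | 42.3% | 59.0% | 18.1% |

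In the later-onset 50/28 mg arm of up to 16, with the same p at baseline and k = 7, the expected number in the at-least-one row is 16 × (1 − p) × P. That is 16 × 0.99 × 0.068 = 1.1 at 1% and 16 × 0.80 × 0.790 = 10.1 at 20%. The at-least-two row runs from 0.0 to 5.4. The expected number positive at baseline is 16 × p, or 0.2 to 3.2 children.

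**The case against.** Most of the case against concerns how far the point can be pushed, and much of it stands.

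A reader might infer that a child going from trace to +4 is never counted. The documents do not support that. The child is counted as positive at baseline and every value is listed. The shift-to-abnormal display would also capture the child if trace is not abnormal there. With up to 16 + 8 = 24 later-onset participants, a +4 can be found by reading the listing. That does not make the listing a comparison by arm, and it is less practical with about 75 infantile-onset participants or up to about 40 in Part C.

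A reader might also infer that background trace results fill the table. This is a prediction, not something the documents show. Over the assumed rates the effect runs from slight to dominant, and the at-least-two row dampens it strongly (4.4% against 30.2% at p = 5%, k = 7). In Part B the randomised 12 mg arm carries the same background, so isolated traces add noise and do not by themselves create or hide a difference. Part C has no control arm, so that reassurance does not apply there.

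Nor does the SAP say that only numeric results are summarised. The general categorical rule could yield grade percentages by visit.

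Finally, negative versus any positive with a repeat-positive row is a reasonable sensitive screen for new proteinuria, and nothing in the SAP contradicts it. That is true, but a screen for new positives is narrower than the change endpoint it serves.

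**Conclusion.** The structural point holds at any background rate. The dedicated urine protein table registers 5 of 15 possible upward moves, does not separate those 5 by size, and shows no worsening from a positive baseline. No other planned display explicitly links a subject's baseline grade to the worst later grade by arm.

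The number of subjects affected cannot be stated from the documents. Under the assumed 1% to 20% baseline positivity, it is between none and about 3 of 16 in the later-onset 50/28 mg arm. The effect of isolated trace results on the counts is likewise unknown.

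This is a weakness in one descriptive safety display for a named endpoint. It affects no hypothesis test, sample size or efficacy conclusion. It is worth correcting because the correction is nearly free.

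**What to change.** Add to, or replace, the three counts with a shift table from baseline grade (negative, trace, +1, +2, +3, +4) to worst post-baseline grade. Present it by arm in Part B and by study group in Part C, using all post-baseline results as the SAP's other shift tables do. Count any rise above the baseline grade as emergent, whatever the baseline grade, and put rises that reach only trace on a separate row. Use the same table in the Part B infantile-onset, Part B later-onset and Part C SAPs.

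Numeric results need no new display, since the change-from-baseline summaries already cover them. It would help to state in the same place whether trace is abnormal in the urinalysis shift display.

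The cost is one table shell, programmed once and used three times, from data already collected.

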# 6.1.3. Neurological Examinations

Neurological examinations include assessment of mental status, level of consciousness, cranial nerves, reflexes, motor system, coordination/cerebellar function and sensation – temperature and vibration. These are to be assessed at Screening, predose and at 3, 6, and 24 hours postdose on dosing Days 1, 15, predose and at 1 and 3 hours postdose on Days 29, 64, 135, 183, and 279; and at Day 302/ET.

The results collected for the majority of the tests are classified as 'normal' or 'abnormal', however the assessment of sensations is reported as 'present' or 'absent' and the assessment of reflexes is captured on an ordinal scale. For each test it is recorded if secondary to SMA.

#### Acute Effects After Dosing: Reflex assessments

On each dosing day, each predose reflex will be compared with all the post dosing assessments with 24 hours to see if the subject has changed (gained or lost) or maintained, reflexes. For this comparison the predose reflex status will be categorized into two categories: 0 and  $\geq 1$ . For each

Product: Nusinersen	Statistical Analysis Plan
Study: 232SM203	Version: 1.0

reflex, visit, predose category the number and proportion of subjects who change or maintained will be presented.

#### Acute Effects After Dosing: Other assessments with binary response (Normal/Abnormal)

On each dosing day, the shifts from predose assessment on that day to postdose (i.e., from predose to 3, 6 and 24 hours postdose) will be determined. For each test and post dosing time point, the number and proportion of subjects who moved from 'Normal' to 'Abnormal' will be presented, for sensations the number and proportion who move from 'Present' to 'Absent' will be presented.

#### **Chronic effects: Reflex assessments**

For each reflex the baseline reflex will be compared (the predose value on Day 1) to the pre dose value on later dosing days (Day 1, 15, 29, 64, 135,183, 279 and on Day 302/ET) to see if the subject has changed (gained or lost) or maintained, reflexes. For this comparison the predose reflex status will be categorized into two categories: 0 and  $\geq 1$ . For each reflex, visit, predose category the number and proportion of subjects who change or maintained will be presented.

#### Chronic effects: Other assessments with binary response (Normal/Abnormal)

For each test the shift from baseline to (the predose value on Day 1) the predose value on later dosing days (Day 1, 15, 29, 64, 135, 183, 279 and on Day 302/ET) to determine, the number and proportion of subjects who moved from 'Normal' to 'Abnormal' will be presented, for sensations the number and proportion who move from 'Present' to 'Absent' will be presented.

Figures of subjects neurological exams will also presented.

#### 6.1.4. ECG

ECGs are to be recorded at Days 1, 15, 29, 64, 135, 183, 279 and 302/ET, predose and post dosing at various time points on dosing days and end predose at 302/ET. The ECGs are assessed at a central reading laboratory and the results provided as external vendor data. On the eCRF the investigator interpretation is collected as normal, abnormal and abnormal AE and the investigator determination will be used in analyses.

The ECG test includes heart rate, QT interval, QTcF interval and RR interval. Summary statistics for actual values and change from baseline in each ECG parameter will be presented by treatment group and visit.

ECGs will be analyzed using two approaches.

#### Qualitative analysis

The determination of whether an ECG is abnormal not AE, abnormal AE made by the Investigator will be used for this qualitative analysis.

The number and percentage of subjects with shifts from normal to each of the categorical values denoting an abnormal scan (abnormal not AE, abnormal AE) will be summarized by treatment group. All post baseline data will be used to identify abnormalities, regardless of whether a scheduled or unscheduled visit.

Product: Nusinersen	Statistical Analysis Plan
Study: 232SM203	Version: 1.0

#### **Corrected Fridericia QT interval QTcF abnormalities (outliers)**

QTcF will be examined to determine the incidence of clinically relevant abnormalities. The number of subjects evaluated and the number of subjects with clinically relevant abnormalities will be presented.

The first criteria for clinically relevant post dosing abnormalities (secondary safety endpoint) that will be considered is:

• Post baseline QTcF of > 500 msec and Maximum increase from baseline to post baseline QTcF >60 msec

Other criteria are:

- Maximum increase from baseline QTcF > 30 to 60 msec
- Maximum increase from baseline QTcF > 60 msec
- Maximum post baseline QTcF > 480 to 500 msec
- Maximum post baseline QTcF > 500 msec

ECG summaries will be presented for all subjects and for subjects with post baseline. Listings will include both the central and eCRF information.

